## 10. Study Procedures and Assessments

### 10.1 Clinical Study Schedule

Study Visit	Screening	Medical instrument application	Assessment
	Visit1 	Visit2 	
Day	-2W-Day1	Day1	
Obtain agreement letter 	O		
Screening numbering	O		
Check selection/exclusion criteria 	O		
Obtain demographic information 	O		
Check medication taken or under taking 	O		
Measure wrist circumference	O		
Check circumference of upper arm	O		
Measure blood pressure		O (H2-BP, stethoscope type blood pressure gauge)	O
Check taking medication		O	
Check abnormal examples 		O	

- 1) Any procedure in this observatory study shall not start before having patient's agreement letter (Letter of consent on using information). Voluntary agreement shall be made preferentially by the patient, but for impossibility of making the agreement letter due to emergencies (Endotracheal intubation and cardio pulmonary resuscitation), the agreement letter may be obtained from the legal proxy person. In this case, additional agreement letter shall be taken from the patient after stabilization or finalization of the emergent situation to the patient.
- 2) Check the selection/exclusion criteria, obtain demographic information, check the medication taken in advance or under taking and measure the wrist circumference and circumference of upper arm after screening numbering.
- 3) Demographic survey: Survey the demographic information (Date of birth, age and gender).
- 4) Check the medication taken in advance or under taking: Collect overall information on advanced medication and taken medication before applying the clinical study medical instrument from 2 weeks before screening till applying clinical study medical instrument.
- 5) Survey the abnormal reactions from the first test related procedure (Namely, signing date of the patient on the agreement letter) till the last assessment date.
- 6) Screening the visit and the medical instrument applying visit can be processed concurrently.

### 10.2 Observational Examination Method for Subjects Using the Investigational Device

#### 1) Assignment of Screening and Enrollment Numbers

A Screening Number shall be assigned only to subjects who have provided written informed consent for participation in this clinical trial. Screening numbers will be assigned in the order of consent acquisition. If multiple subjects provide consent on the same day, the screening numbers will be assigned based on the order of arrival.

The Screening Number shall consist of a single-digit site identifier, the letter 'S' (indicating Screening), and a three-digit sequential subject number, assigned according to the following method

Site Number	S	-	Three-digit number assigned sequentially based on Screening order
Gangnam Severance Hospital: 1	S	-	001,002,003, ...
Example: The Screening Number for the first subject screened at Gangnam Severance Hospital is 1S-001.			

For subjects enrolled after Screening, an Enrollment Number will be assigned, consisting of a single-digit site identifier, the letter 'R' (indicating Registration), and a three-digit sequential subject number, according to the method described below. The target sample size will be counted based on the number of enrolled subjects, regardless of the total number of screened subjects.

Site Number	R	-	Three-digit number assigned sequentially based on Screening order
Gangnam Severance Hospital: 1	R	-	001,002,003, ...

**Example:** The Screening Number for the first subject screened at Gangnam Severance Hospital is 1R-001.

## 2) Demographic Data Collection

At the time of Screening (Visit 1), detailed demographic information of the subject will be collected and recorded. The demographic data will include the subject's date of birth, age, and gender.

## 3) Adverse Event Monitoring

The investigator will observe for the occurrence of adverse events (AEs) throughout the clinical study period, starting from Visit 2 (application of the investigational medical device). Any adverse events identified will be documented in the Case Report Form (CRF), including the onset date, resolution date, severity, causal relationship, and actions taken.

## 4) Concomitant Medication Monitoring

Information on all prior medications administered within 2 weeks prior to Screening (Visit 1) and before the application of the investigational device, as well as on concomitant medications administered after the application of the investigational device, will be collected. For both prior and concomitant medications, the following details will be recorded: drug name (active ingredient), purpose of administration, daily dosage, route of administration, and duration of administration.

### 10.3 Clinical Study Schedule

#### 1) Visit 1 (Screening, Day 0)

Complete the following Screening procedures before the application of the investigational device:

1. Obtain written informed consent from the subject or their legal representative (proxy) prior to conducting any study procedures.
2. Assign a Screening number after obtaining the subject's consent.
3. Review the inclusion and exclusion criteria following the assignment of the Screening number.
4. Collect demographic information.
5. Verify prior/concomitant medications.

6. Measure the wrist circumference.
7. Measure the upper arm circumference.

## 2) Visit 2 (Day 1)

Subjects assigned a Screening number and enrolled in the clinical trial will undergo the application of the investigational device on Day 1. Note that the Screening date and Day 1 may occur on the same day.

1. Measure blood pressure using the H2-BP device and an auscultatory blood pressure monitor.
2. Verify concomitant medications.
3. Monitor for adverse events (AEs).

## 11. Effectiveness Evaluation Parameter

Evaluate the accuracy by adopting the following evaluation parameters by measuring the blood pressure in three times at systolic and diastolic area from total 141 subjects. The qualification decision shall be pursuant to the following criteria. (The minimum subjects shall be over 85 and measured data shall be over 255 cases.)

### 11.1 Primary Endpoint

(1) Average on difference between blood pressures measured with investigational device and comparator

n=Count of measurement Ex) For 85 subjects-> n=255

i is a separate index for count of measurement.

$$p_{\text{comparator-}sq_i} = \frac{1}{4} \times (p_{\text{comparator}_{i,1}} + p_{\text{comparator}_{i,2}} + p_{\text{comparator}_{i+1,1}} + p_{\text{comparator}_{i+1,2}})$$

$p_{\text{comparator}_{i,1}}$  is the blood pressure data measured at i – th time by the operator 1

$p_{\text{comparator}_{i,2}}$  is the blood pressure data measured at i – th time by the operator 2

[Formula for calculating the primary endpoint]

$$\text{Average of difference}(\bar{x}_n) = \frac{1}{n} \times \sum_{i=1}^n (p_{\text{Investigational device}_i} - p_{\text{comparator-}sq_i})$$

Corresponding endpoint shall have error range less than  $\pm 0.67$  kPa.

(2) Standard deviation on the blood pressures measured with investigational device and comparator. (Based on count of measurement)

n= Count of measurement Ex) For 85 subjects -> n=255

i is a separate index for count of measurement.

[Formula for calculating the primary endpoint]

$$\text{Standard deviation of difference based on count of the measurements} (s_n) = \sqrt{\frac{1}{n-1} \times \sum_{i=1}^n (x_i - \bar{x}_n)^2}$$

Corresponding endpoint shall have error range less than 1.07 kPa.

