### 9.1 Implementation of Monitoring for Subjects Using the Investigational Device

For subjects undergoing monitoring (or their legally authorized representatives, if applicable), screening shall be conducted after obtaining written informed consent for participation in the clinical study. Based on the screening assessment, subjects who meet the inclusion criteria and do not meet the exclusion criteria will be enrolled in the study.

Blood pressure measurements will be performed in a seated position, alternating between the investigational device and the comparator device. The measurement procedure follows the steps below:

1. Using the comparator device, one valid pair of systolic and diastolic blood pressure (BP) values will be obtained from the upper arm as shown in Figure 1.
2. The investigational device will then be applied to the same arm's wrist, and one valid pair of systolic and diastolic BP values will be obtained.
3. Steps 1 and 2 will be repeated until three valid pairs of BP values are collected for each subject. A minimum interval of 60 seconds will be maintained between each measurement.
4. The same procedure will be followed for all other enrolled subjects.

[figure not shown]

Figure 1. ①Stethoscope ②Comparator Device Manometer ③Pump ④Investigational Device

The investigational device measurement is recorded by a single operator. In contrast, the comparator device measurement is recorded by two independent operators, each using a separate stethoscope to simultaneously assess and document the blood pressure readings.

When measuring diastolic blood pressure (DBP) using auscultation, Korotkoff Phase V should be recorded. If Korotkoff Phase V is not audible, the subject shall be excluded from the study.

The two operators using the auscultatory blood pressure measurement method must conduct their measurements independently, ensuring that they cannot communicate or be aware of each other's recorded values for each subject. Additionally, during the measurement process, the operators must not have access to the investigational device's readings.

\* If the difference between the two simultaneous measurements exceeds the following thresholds, the corresponding blood pressure value pair shall be excluded:

- If the systolic blood pressure (SBP) difference between the two operators is greater than 4 mmHg, the value pair is excluded.

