## 11.2 Secondary Endpoint

(1) Standard deviation on difference between blood pressures measured with investigational device and comparator. (Based on the count of the subjects)

m= Count of measurement Ex) For 85 subjects -> n=255

j is a separate index for count of measurement.

d is the count of measurement per experimentee.

k is an index for the individual factor.

$$x_j = \frac{1}{d} \times \sum_{k=1}^d (p_{\text{investigational device}_{j,k}} - p_{\text{comparator-}sq_{j,k}})$$

$$p_{\text{comparator-}sq_{j,k}} = \frac{1}{4} \times (p_{\text{comparator}_{j,k,1}} + p_{\text{comparator}_{j,k,2}} + p_{\text{comparator}_{j,k+1,1}} + p_{\text{comparator}_{j,k+1,2}})$$

[Formula for calculating the secondary endpoint]

$$\text{Standard deviation of difference based on count of the subjects} (s_m) = \sqrt{\frac{1}{m-1} \times \sum_{j=1}^m (x_j - \bar{x}_n)^2}$$

The secondary endpoint shall meet the Table 1 or 2 based on ISO 81060-2 standard depending on the blood pressure data.

Table 1 – Average subject data acceptance (criterion 2) in mmHg

$\bar{x}_n$	Maximum permissible standard deviation, $s_m$ , as function of, $\bar{x}_n$ mmHg									
	0,0	0,1	0,2	0,3	0,4	0,5	0,6	0,7	0,8	0,9
$\pm 0,$	6,95	6,95	6,95	6,95	6,93	6,92	6,91	6,90	6,89	6,88
$\pm 1,$	6,87	6,86	6,84	6,82	6,80	6,78	6,76	6,73	6,71	6,68
$\pm 2,$	6,65	6,62	6,58	6,55	6,51	6,47	6,43	6,39	6,34	6,30
$\pm 3,$	6,25	6,20	6,14	6,09	6,03	5,97	5,89	5,83	5,77	5,70
$\pm 4,$	5,64	5,56	5,49	5,41	5,33	5,25	5,16	5,08	5,01	4,90
$\pm 5,$	4,79	-	-	-	-	-	-	-	-	-

Example For mean of  $\pm 4,2$ mmHg the maximum permissible standard deviation is 5,49 mmHg.

Table 2 – Average subject data acceptance (criterion 2) in kPa

$\bar{x}_n$	Maximum permissible standard deviation, $s_m$ , as function of, $\bar{x}_n$ kPa									
	0,000	0,010	0,020	0,030	0,040	0,050	0,060	0,070	0,080	0,090
$\pm 0,0$	0,9266	0,9266	0,9266	0,9266	0,9226	0,9246	0,9233	0,9223	0,9213	0,9203
$\pm 0,1$	0,9193	0,9183	0,9173	0,9163	0,9152	0,9138	0,9119	0,9099	0,9079	0,9059
$\pm 0,2$	0,9039	0,9007	0,8989	0,8970	0,8946	0,8906	0,8878	0,8855	0,8826	0,8785
$\pm 0,3$	0,8756	0,8723	0,8679	0,8641	0,8601	0,8562	0,8519	0,8471	0,8414	0,8374
$\pm 0,4$	0,8333	0,8283	0,8226	0,8169	0,8119	0,8059	0,7999	0,7933	0,7853	0,7793
$\pm 0,5$	0,7739	0,7669	0,7599	0,7531	0,7463	0,7388	0,7319	0,7237	0,7157	0,7077
$\pm 0,6$	0,6999	0,6891	0,6802	0,6723	0,6670	0,6595	0,6488	0,6386	-	-

Example For mean of  $\pm 0,520$ kPa the maximum permissible standard deviation is 0,7599 kPa.

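### The Section 11.1 primary formula has no subject index, so as printed one reference in three borrows half its value from the next subject and s_n is inflated

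*Combined protocol and SAP*

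**What the plan says.** Section 11.1 holds both parts of the primary endpoint. It sets the number of differences, "n=Count of measurement Ex) For 85 subjects-> n=255", and describes the subscript by "i is a separate index for count of measurement". A comparator value with subscripts i and 1 "is the blood pressure data measured at i – th time by the operator 1"; subscript 2 is the second operator. The reference for device reading i is the mean of four values: both operators at comparator readings i and i+1. The same i stands on the H2-BP reading, and the sum runs from 1 to n. No subscript identifies the subject. The s_n formula uses a term x_i that 11.1 does not define.

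The pass limits follow directly. For the mean: "Corresponding endpoint shall have error range less than $\pm 0.67$ kPa". For s_n: "Corresponding endpoint shall have error range less than 1.07 kPa".

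Section 11.2 builds the same four-value reference with two subscripts, j and k, and averages over k from 1 to d, where "d is the count of measurement per experimentee". Its labels are loose: it calls k by the words "k is an index for the individual factor", and it describes m and j as measurement counts with n=255, although s_m is an SD over subjects.

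Section 9.1 takes a comparator reading (step 1), then a device reading (step 2), and continues: "Steps 1 and 2 will be repeated until three valid pairs of BP values are collected for each subject". Section 15.2 repeats the endpoint names and adds no formula.

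**The concern.** If i counts measurements across the whole trial, i+1 is simply the next comparator reading in the list. At each subject's last reading, that is the first reading of a different person. The difference then contains half the gap between two people's blood pressures, which is not device error.

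This affects a pass/fail criterion. The distribution criteria in Section 9.1 require a wide range of pressures across subjects, and that range is what would leak into s_n. An accurate device could exceed the 1.07 kPa limit because of the indexing. The formula also cannot be completed for the last reading, so a programmer would have to repair the primary endpoint after data exist.

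**Working it through.** **Inputs from the documents.** 85 subjects, 255 measurements and limits of 0.67 and 1.07 kPa (Section 11.1); three comparator and three device readings per subject, comparator first (Section 9.1); the pressure distribution criteria (Section 9.1).

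**Assumed, because the documents give no values.** The correctly paired SD, s (5 mmHg, with 6 and 7 as alternatives); the between-subject SD, σ (range shown below); subjects in unrelated order.

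**The plan's own figure.** 85 × 3 = 255, as stated. At 7.50062 mmHg per kPa, the limits are 0.67 kPa = 5.03 mmHg and 1.07 kPa = 8.03 mmHg.

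**Which readings are paired.** Number both devices' readings three per subject.
- Subject 1 owns i = 1, 2, 3; subject 2 owns 4, 5, 6; and so on.
- At i = 1 and 2, comparator i+1 belongs to the same subject. At i = 3 it is reading 4, which belongs to subject 2.
- The same happens at i = 3, 6, ..., 252, which is 252/3 = 84 differences. In each, two of the four averaged values come from the next subject.
- At i = 255 the formula asks for comparator reading 256, which does not exist.

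**Effect on s_n.** In an affected difference, the reference is shifted by half the gap between two subjects' pressures. The variance of that shift is (1/4) × 2σ² = σ²/2. About one third of differences are affected, so

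s_n² ≈ s² + (1/3)(σ²/2) = s² + σ²/6.

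With the exact share among the 254 computable differences, the factor is (84/254)/2 = 0.165.

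**Plausible σ for SBP.**
- Smallest spread that meets the criteria: 5% of values at 100, 5% at 160, 15% at 140 and 75% at 136. The mean is 136 and the variance (5×36² + 5×24² + 15×4²)/100 = 96, so the SD is 9.8. This is the SD of all readings, used here as a proxy for σ.
- Normal distribution with exactly 5% at or below 100 and 5% at or above 160: 60/(2 × 1.645) = 18.2.

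**Results for SBP at s = 5 mmHg (factor 0.165, limit 8.03).**

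| σ (mmHg) | s_n (mmHg) | Against the limit |
|---|---|---|
| 9.8 | √(25 + 15.9) = 6.4 | passes |
| 15.4 | √(25 + 39.2) = 8.0 | at the limit |
| 18.2 | √(25 + 54.8) = 8.9 | fails on average |

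At σ = 18.2, simulated trials of 85 subjects (device error SD 3.5 between and 3.57 within subjects, perfect reference, stable pressure) pass in about 8% of runs. With correct pairing the same device has s_n of about 5.0. For s = 6 and s = 7, s_n reaches the limit at σ of about 13.1 and 9.6.

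**DBP.** The normal calculation gives σ = 40/(2 × 1.645) = 12.2 and s_n of about 7.0; about 98% of simulated trials pass. At the minimum spread (σ = 6.4), s_n is about 5.6.

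**Effect on the mean.** The cross-subject terms telescope: their sum is half the pressure gap between the last and first subjects, divided by 254 differences. At σ = 18.2 this has an SD of 18.2 × √2/508 = 0.05 mmHg, against a limit of 5.03.

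**Does re-indexing alone suffice?** With the order C1, D1, C2, D2, C3, D3, reading D1 lies between C1 and C2, and D2 between C2 and C3. D3 has no later comparator reading. Only 85 × 2 = 170 of 255 differences can be bracketed within subject; all 255 would need 85 × 4 = 340 comparator readings.

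**The case against.** The strongest reply is that no competent analyst would pair across subjects. Section 2 asks for three valid pairs from each subject, Section 9.1 completes the sequence on one subject before the next, and 11.2 averages within j. Section 11.2 also uses the 11.1 mean in s_m, so both sections are meant to share one difference. A literal run would stop at reading 256 and expose the error, and the bias works against the sponsor, since it cannot help an inaccurate device to pass. Further, if 11.2's mislabelled m and j are read by their evident intent, 11.1 deserves the same courtesy.

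Much of this stands, and it limits the point. A reader might infer that the trial's primary result will be wrong, or that 11.1 and 11.2 deliberately set two different references. The documents do not support either: the four-value average has the same name in both places, and the intended pairing is clear. A reader might also infer that the mismatch would be almost total, by imagining a fourth comparator reading per subject under the same running index. Section 9.1 schedules no such reading, so that case is not evidence about this plan. Nor is the mean criterion materially affected.

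What remains is that the printed primary formula is wrong for the readings that Section 9.1 schedules. Section 11.2 is not a clean fallback, because its labels are wrong and its reference also needs reading k+1 when k = 3.

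**Conclusion.** The point holds as an error in the printed definition of the primary endpoint. As written, 84 of 255 references are half another subject's pressure and one cannot be computed. That part is simple counting and needs no assumption beyond numbering the readings in the order of Section 9.1.

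The size of the effect on s_n does rest on assumptions. For a correctly paired SD of 5 mmHg, SBP s_n goes from comfortably passing (6.4) at the minimum spread that the plan allows to failing (8.9) at the spread implied by normal 5% tails, crossing the limit near σ = 15.4. The normal case is not the least spread that meets the criteria, so 18.2 is illustrative. DBP stays within the limit at s = 5 in both cases. The direction is a false fail.

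The text should be corrected before the analysis. It does not show that the analysis will be run incorrectly.

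**What to change.** 1. Rewrite 11.1 with j for subject and k for reading within subject: x_{j,k} = p_device_{j,k} − ¼(p_comp_{j,k,1} + p_comp_{j,k,2} + p_comp_{j,k+1,1} + p_comp_{j,k+1,2}), with k+1 always within subject j. Take the mean and s_n over all j and k, and state that x_i in the s_n formula is this difference.
2. Use the same difference in 11.1, 11.2 and the Bland-Altman plots of 15.4.
3. In 11.2, correct the labels: j indexes subjects, m is the number of subjects (85 in the example, not n=255), and k indexes readings within a subject.
4. Reconcile the reading sequence in 9.1 with the reference in 11.1 and 11.2, so that the reference is defined for the third device reading. Either the sequence gains a closing comparator reading or the definition of the reference changes; the plan should say which.

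Items 1 to 3 are wording only. Item 4 may not be: an added comparator reading changes the procedure for every subject, and without one only 170 of the 255 differences can be bracketed as the formula requires.

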## 11.2 Secondary Endpoint

(1) Standard deviation on difference between blood pressures measured with investigational device and comparator. (Based on the count of the subjects)

m= Count of measurement Ex) For 85 subjects -> n=255

j is a separate index for count of measurement.

d is the count of measurement per experimentee.

k is an index for the individual factor.

$$x_j = \frac{1}{d} \times \sum_{k=1}^d (p_{\text{investigational device}_{j,k}} - p_{\text{comparator-}sq_{j,k}})$$

$$p_{\text{comparator-}sq_{j,k}} = \frac{1}{4} \times (p_{\text{comparator}_{j,k,1}} + p_{\text{comparator}_{j,k,2}} + p_{\text{comparator}_{j,k+1,1}} + p_{\text{comparator}_{j,k+1,2}})$$

[Formula for calculating the secondary endpoint]

$$\text{Standard deviation of difference based on count of the subjects} (s_m) = \sqrt{\frac{1}{m-1} \times \sum_{j=1}^m (x_j - \bar{x}_n)^2}$$

The secondary endpoint shall meet the Table 1 or 2 based on ISO 81060-2 standard depending on the blood pressure data.

Table 1 – Average subject data acceptance (criterion 2) in mmHg

$\bar{x}_n$	Maximum permissible standard deviation, $s_m$ , as function of, $\bar{x}_n$ mmHg									
	0,0	0,1	0,2	0,3	0,4	0,5	0,6	0,7	0,8	0,9
$\pm 0,$	6,95	6,95	6,95	6,95	6,93	6,92	6,91	6,90	6,89	6,88
$\pm 1,$	6,87	6,86	6,84	6,82	6,80	6,78	6,76	6,73	6,71	6,68
$\pm 2,$	6,65	6,62	6,58	6,55	6,51	6,47	6,43	6,39	6,34	6,30
$\pm 3,$	6,25	6,20	6,14	6,09	6,03	5,97	5,89	5,83	5,77	5,70
$\pm 4,$	5,64	5,56	5,49	5,41	5,33	5,25	5,16	5,08	5,01	4,90
$\pm 5,$	4,79	-	-	-	-	-	-	-	-	-

Example For mean of  $\pm 4,2$ mmHg the maximum permissible standard deviation is 5,49 mmHg.

Table 2 – Average subject data acceptance (criterion 2) in kPa

$\bar{x}_n$	Maximum permissible standard deviation, $s_m$ , as function of, $\bar{x}_n$ kPa									
	0,000	0,010	0,020	0,030	0,040	0,050	0,060	0,070	0,080	0,090
$\pm 0,0$	0,9266	0,9266	0,9266	0,9266	0,9226	0,9246	0,9233	0,9223	0,9213	0,9203
$\pm 0,1$	0,9193	0,9183	0,9173	0,9163	0,9152	0,9138	0,9119	0,9099	0,9079	0,9059
$\pm 0,2$	0,9039	0,9007	0,8989	0,8970	0,8946	0,8906	0,8878	0,8855	0,8826	0,8785
$\pm 0,3$	0,8756	0,8723	0,8679	0,8641	0,8601	0,8562	0,8519	0,8471	0,8414	0,8374
$\pm 0,4$	0,8333	0,8283	0,8226	0,8169	0,8119	0,8059	0,7999	0,7933	0,7853	0,7793
$\pm 0,5$	0,7739	0,7669	0,7599	0,7531	0,7463	0,7388	0,7319	0,7237	0,7157	0,7077
$\pm 0,6$	0,6999	0,6891	0,6802	0,6723	0,6670	0,6595	0,6488	0,6386	-	-

Example For mean of  $\pm 0,520$ kPa the maximum permissible standard deviation is 0,7599 kPa.

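### Section 11.2, Table 2 has one out-of-order limit (mean 0.040 kPa), and the plan fixes neither the deciding unit nor the lookup rule, so a borderline verdict can depend on the table used

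*Combined protocol and SAP*

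**What the plan says.** All references are to the combined protocol and SAP. The tables print decimal commas; decimal points are used here.

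- **Section 11.1** gives the primary limits in kPa only. The mean difference must be below ±0.67 kPa. For the measurement-level SD: "Corresponding endpoint shall have error range less than 1.07 kPa".
- **Section 11.2** gives the limit for the subject-level SD as a function of the mean difference, and prints it twice, in mmHg (Table 1) and in kPa (Table 2). The rule is: "The secondary endpoint shall meet the Table 1 or 2 based on ISO 81060-2 standard". A closing clause of the same sentence makes the choice of table depend on the blood pressure data.
- **Worked examples in Section 11.2.** For a mean of ±4.2 mmHg, "mmHg the maximum permissible standard deviation is 5,49 mmHg". For a mean of ±0.520 kPa, "kPa the maximum permissible standard deviation is 0,7599 kPa".
- **Section 9.1** states its rules on reading pairs in mmHg, for example: "If the systolic blood pressure (SBP) difference between the two operators is greater than 4 mmHg, the value pair is excluded". Its criteria for the spread of reference pressures are also in mmHg.

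No section says which unit decides, or how to read a table when the mean falls between two printed values.

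**The concern.** Section 11 makes these limits the basis of the qualification decision, so each should have one value and be fixed before the data are seen. Two features work against that.

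First, a limit on the SD should not loosen as the mean error grows. In the first row of Table 2 it does, once. As printed, an SD of 0.9239 kPa (6.93 mmHg) fails at a mean of 0.040 kPa but passes at the larger mean of 0.050 kPa.

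Second, the clause that selects the table can be read as pointing to the unit of the data, but the plan does not say what that unit is. The reading-pair rules are in mmHg and the primary limits in kPa, so a mean held in mmHg has to be converted to test Section 11.1. After that, either table can be entered. Where the two tables, or two ways of reading them, give different limits, a result close to the limit can pass one and fail the other.

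**Working it through.** **Inputs.** Tables 1 and 2 (51 and 68 printed limits) from Section 11.2; 0.67 and 1.07 kPa from Section 11.1. The conversion 1 mmHg = 0.133322 kPa is a physical constant that the plan does not state.

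**1. The plan's own examples reproduce across units.**
- 5.49 mmHg × 0.133322 = 0.7319 kPa. The mean of 4.2 mmHg is 0.560 kPa, where Table 2 prints 0.7319.
- 0.7599 kPa ÷ 0.133322 = 5.70 mmHg. The mean of 0.520 kPa is 3.90 mmHg, where Table 1 prints 5.70.

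**2. Order.** Neither table should rise as the mean grows. Table 1 never does. Table 2 does exactly once:

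| Mean (kPa) | Mean (mmHg) | Table 2 (kPa) | Table 2 in mmHg | Table 1, interpolated (mmHg) | Gap (mmHg) |
|---|---|---|---|---|---|
| 0.030 | 0.225 | 0.9266 | 6.950 | 6.950 | 0.000 |
| 0.040 | 0.300 | 0.9226 | 6.920 | 6.950 | −0.030 |
| 0.050 | 0.375 | 0.9246 | 6.935 | 6.935 | 0.000 |

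Table 1 at 0.3 mmHg converts to 6.95 × 0.133322 = 0.9266 kPa, so the printed cell is 0.0040 kPa too strict relative to Table 1.

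**3. All other cells.** Of the 68 Table 2 cells, 67 lie within the range of Table 1. Comparing each, in mmHg, with Table 1 linearly interpolated at the same mean:
- 61 agree within 0.010 mmHg and 66 within 0.022 mmHg; the mean absolute gap is 0.003 mmHg.
- The one cell outside 0.022 mmHg is the cell at 0.040 kPa.
- The other gaps above 0.010 mmHg (0.013 to 0.022) are at means of 0.61–0.63 and 0.65–0.66 kPa.

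**4. Lookup rule.** With interpolation in both tables, the limits differ by at most 0.030 mmHg (at a mean of 0.3 mmHg), and by 0.026 mmHg at a mean of 5.0 mmHg. With nearest-cell reading they can differ by up to 0.08 mmHg for means of about 4.5 to 5.0 mmHg, because the grids do not coincide. Example: a mean of 4.538 mmHg is 0.605 kPa. Table 1 is read at 4.5 mmHg (5.25 mmHg). Table 2 is read at 0.61 kPa (0.6891 kPa = 5.169 mmHg). The difference is 0.081 mmHg.

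**5. Upper edge.** 0.67 ÷ 0.133322 = 5.025 mmHg, whereas Table 1 stops at 5.0 mmHg (0.6666 kPa). A mean between 5.00 and 5.025 mmHg meets Section 11.1 and lies within the range of Table 2, but beyond the last Table 1 entry. The last limits themselves agree: 0.6386 kPa = 4.79 mmHg. For reference, 1.07 kPa = 8.026 mmHg.

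**The case against.** Four points can be made for the plan.

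- **The cell may be a copying or reading slip.** It differs from its left-hand neighbour in one digit, and neither the cited standard nor an image of the page was available to settle it. That is a reason to check the cell against the source; it does not remove the contradiction as printed. The cell is also stricter than Table 1, so it cannot by itself pass a device that Table 1 would fail.
- **The rule ties the table to the data.** The clause at the end of the sentence is naturally read as meaning the unit of the data, and Section 9.1 points to mmHg. This stands in part: a reader might infer a free choice of table after the result is known, and the text does not say that. It is vague rather than open, because the unit is never named.
- **The upper edge may not matter.** If means are rounded to the nearest cell, those from 5.00 to 5.025 mmHg fall on the last cell of both tables and meet the same 4.79 mmHg limit. A mean of exactly 0.670 kPa already fails Section 11.1, which requires less than 0.67. So the mismatch bites only under other lookup rules, such as interpolation, and the plan specifies none.
- **The size is negligible beside sampling error.** With the minimum 85 subjects and normal errors assumed, the standard error of an SD near 6.95 mmHg is about 6.95/√(2 × 84) = 0.54 mmHg. The 0.030 mmHg gap is about one eighteenth of that. This stands, and it sets the weight of the point.

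**Conclusion.** The point holds as a minor inconsistency. One printed threshold, Table 2 at 0.040 kPa, conflicts with its neighbours and with Table 1, and the plan leaves the deciding unit and the lookup rule unstated. A verdict could change only in narrow strips:

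- absolute mean of about 0.23–0.37 mmHg with a subject-level SD of about 6.92–6.95 mmHg;
- absolute mean of about 4.5–5.0 mmHg with an SD within about 0.02–0.03 mmHg of the limit if both tables are interpolated, or 0.08 mmHg if the nearest cell is read;
- absolute mean from 5.00 up to 5.025 mmHg, depending on the lookup rule.

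A reader might go further in three ways that the documents do not support. The two tables do not disagree in general: they are near-exact conversions of each other. The Section 11.1 limits do not conflict with an mmHg version, because they appear in kPa only. And stating a reading-pair rule in mmHg and an acceptance limit in kPa is not in itself an error.

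The conclusion rests on the standard conversion factor and on the table digits as they appear in the text.

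**What to change.** 1. Check the 0.040 kPa cell of Table 2 against the source standard and correct it, or drop Table 2. Any value from 0.9246 to 0.9266 kPa restores the order; Table 1 converts to 0.9266.
2. Name one deciding unit for Sections 11.1 and 11.2 before analysis, and make the other unit informational only.
3. State how a mean between grid points is handled (rounding or interpolation), and to how many decimals the mean and SD are carried before comparison.
4. Align the mean limit in Section 11.1 with the end of the chosen table. If kPa is chosen, 0.67 already matches the last Table 2 entry and only the treatment of exact equality needs stating. If mmHg is chosen, 5.0 and 8.0 mmHg are the natural candidates. They are rounded conversions, not figures printed in Section 11.1, and would tighten the limits by 0.025 mmHg (5.025 − 5.0) and 0.026 mmHg (8.026 − 8.0).

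The cost is a few lines in Sections 11.1 and 11.2. No subjects, measurements or procedures change.
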